2.3 Other Pre-Specified Outcomes

[figure not shown]
All other outcome measures will be exploratory.

3 STUDY DESIGN

3.1 Study Design

The study is a randomized clinical pilot trial that assesses preliminary intervention efficacy of a two session health coaching intervention relative to brief advice among pre-operative elective surgical patients and evaluates intervention feasibility, fidelity, appropriateness, and acceptability. Study subjects will be outpatients at the University of Michigan Health System and fulfill the study's inclusion criteria (see Section 4.1 below). Subjects will be randomized to one of two intervention conditions: Health Coaching or Brief Advice (See Section 5 below).

3.2 Study flow

4 SELECTION AND ENROLLMENT OF PARTICIPANTS

4.1 Inclusion Criteria^{ct.gov;eRsch}

Patients will be eligible for participation if they are: 1) 18 - 75 years of age, 2) referred for elective or semi-elective surgery or pre-operative assessment in the next 120 days, and 3) Meet criteria for “risky drinking,” scoring ≥ 5 on the first 3-items of Alcohol Use Disorders Identification Test (AUDIT). These cutoffs are associated with increased rates of postoperative complications among pre-operative patients following elective surgeries.

4.2 Exclusion Criteria^{ct.gov;eRsch}

Exclusion Criteria.

Patient is...

- 1) unable to provide voluntary informed consent for any reason (including incompetency);
- 2) substantially cognitively impaired as evidenced by lack of orientation to person, place, or time or lack of ability to repeat back and answer screening questions
- 3) Displays or shows evidence of psychotic symptoms
- 4) Unable to read or understand English
- 5) Undergoing surgeries that commonly require local anesthesia only (e.g. cataracts surgery, dental surgery, or other minor surgeries)

4.3 Recruitment^{eRsch}

Given the different structure and patient flow at various pre-operative clinics within Michigan Medicine, participants (N = 90) will be recruited using several methods designed to minimize disruption to patient care. We will seek a waiver of informed consent to identify potentially eligible patients from the medical chart. This waiver will only apply to the initial medical pre-screen for eligibility criteria.

1. In-person recruitment: We will recruit patients in-person from the pre-operative and surgical clinics at Michigan Medicine. Research staff will be given tablets to consent to screening and to complete the screening through Qualtrics. Paper study screening questionnaires will be used as backup and may be distributed by research or clinic staff. The screening assessment will determine patient eligibility to participate in the Phase 3 randomized control trial. The participant will be assigned a random screen ID number. If the participant is eligible and is interested in participating, we conduct the consent process at that time. If this cannot be done right then, eligible subjects will be contacted by study research staff to schedule.

2. Phone recruitment: Patients who have appointments at Michigan Medicine surgical or pre-operative clinics will be identified through MiChart/medical record review. In clinics where we do not recruit in person, the clinics staff will provide patients with a letter at their clinic visit informing (see Phase 3 Patient Invitation Letter) them that they may be contacted by a member of the research team for study participation and give them the option to call the study to ‘opt-out.’ If the clinic cannot provide a letter, we will mail a letter to the patient at least 3 days prior to our recruitment contacts. We are seeking a waiver of consent for this initial medical record screen. Those patients who appear to meet study inclusion/exclusion criteria through MiChart medical review will be contacted by telephone for recruitment (see Study Screening Questionnaire) by study research assistants. They will also be contacted through text or e-mail (see text and e-mail recruitment scripts). The text and e-mail will simply inform them they may be eligible for a research study and include a link to the screening consent form and screening

questions. Those who are eligible will be asked to enter their contact information if they are interested in participating and the research assistant will reach out to them for consent and scheduling. Research assistants will make up to eight contact attempts by phone, text, and e-mail before indicating the patient was “unable to be reached.” We will leave a maximum of three voicemails.

All patients approached either in-person or by phone will be tracked in an Excel spreadsheet. Identifiable information will only be retained for patients that enroll in the study. We will save only medical record numbers (MRNs) for all patients to ensure we do not attempt to recruit them more than once (e.g. if a patient has another surgery and enters into our recruitment list again MRN cross check will allow us to ensure we don’t contact them again). Recruitment outcomes will also be tracked in the Excel spreadsheet to document eligibility, refusals and those the research assistant is unable to reach. Reasons for refusal or ineligibility will also be documented in the Excel spreadsheet.

4.4 Enrollment^{ct.gov}

When the screening survey is administered, the staff member administering the screen will obtain verbal consent (when recruitment by phone) or patients will be asked to agree to the consent on the tablet (if recruiting online). For phone screening the staff member will read aloud the verbal consent script, and obtain verbal consent from the participant before beginning the survey. The oral consent script will contain all information typically included in a written consent document including risk, benefits, and security procedures. Following screening, staff will document the outcome of the call, including: eligible, ineligible, refused, reason for refusal etc.

Participants who meet study eligibility criteria and have not met any of the exclusion criteria, will be given the option to participate in the study. Interested participants will either complete the consent form online or in-person and in all cases will be given the opportunity to ask questions prior to signing the consent. Eligible participants who complete the informed consent in-person will review it with the study research assistant and be given time to read the consent and ask any questions. Patients can also complete the informed consent online, which will contain all of the same information as the paper consent, before an intervention appointment. In all cases participants will be given the opportunity to ask questions before signing the consent. Reasons for refusal will be documented.

Completion of informed consent will be documented and tracked in REDCap. Informed consent documents will be stored in locked files as well as linked to the patient’s data in REDCap. Each participant will be given unique patient identifier in REDCap. Enrolled patients will be tracked in REDCap for surgery details, demographics, recruitment site, randomized intervention type, withdrawals, and intervention completion, and assessment completion.

At the time of the intervention, the research assistant will confirm that the patient is scheduled for surgery and the surgery date.

5 STUDY INTERVENTIONS^{CT.GOV}

The ASPIRE study will offer two conditions that will occur before the patient’s scheduled surgery. The conditions are (1) Health Coaching and (2) Brief Advice. Both interventions will be delivered by a trained member of the research team.

Brief Advice

The Brief Advice session will take place once at least four (4) weeks before the patient's surgery. The Brief Advice session will last approximately 10 minutes. Before the session, the patient will receive the study infographic that visually summarizes the effects of alcohol on surgical health, study recommendations of healthy behaviors, and alcohol use resources. During the session, the patient and trained research team member will refer to the study infographic and discuss alcohol use and health during the pre-operative period. If a participant cannot complete all study activities during one visit, we will allow participants to set an appointment to complete these activities within three days. A staff member at the pre-operative clinic will also give patient's an infographic about alcohol and surgical health during their clinic visit approximately two weeks prior to surgery.

Delivery: The Brief Advice session will be delivered by a trained member of the research team via telehealth or a telephone call, if the patient does not have access to a computer. In both cases, the research team will be using encrypted, university-supported virtual meeting platform with HIPAA-compliant conferencing services to contact the patient. Brief Advice sessions will be audio-recorded for quality assurance purposes. The infographic will be provided at the patient's pre-existing pre-operative clinical visit.

Health Coaching

Health Coaching will consist of two (2) sessions beginning four (4) weeks before the patient's surgery. The sessions will be spaced two (2) weeks apart to accommodate patient response to the intervention. Each Health Coaching session will last approximately 50 minutes. During the Health Coaching sessions, a trained research team member will discuss alcohol use and health during the pre-operative period by using motivational enhancement therapy techniques to improve the patient's motivation to change. Additionally, the research team will provide the patient with alcohol use resources during the Health Coaching sessions. If a participant cannot complete all study activities during one visit, we will allow participants to set an appointment to complete these activities within three days. Follow-up surveys will take place at one-week prior to surgery and one-month post-surgery. A staff member at the pre-operative clinic will also give patient's an infographic about alcohol and surgical health during their clinic visit approximately two weeks prior to surgery.

Delivery: All Health Coaching sessions will be delivered by a member of the research team trained in motivational interviewing. The research team will give patients the option of in-person meetings, or virtual meetings via encrypted, university-supported virtual meeting platform . The Health Coaching sessions will be audio-recorded for quality assurance purposes encrypted, university-supported virtual meeting platform with HIPAA-compliant conferencing services will be used for the videoconferencing or phone meetings. In-person meetings will take place at UM or a building within the UMHS, or a mutually agreed upon location within the community. The infographic will be provided at the patient's pre-existing pre-operative clinical visit.

Intervention Targets (mechanistic and clinical outcomes):

The goal of the pilot trial is to assess the initial efficacy of health coaching relative to brief advice and determine the acceptability and feasibility of both interventions. This study is underpowered to assess mechanisms of change.

Supportive Theories

Supportive theories include social learning theory and motivational interviewing

5.1 Handling of Study Interventions

N/A

5.2 Concomitant Treatment

We will not exclude participants enrolled in other studies and/or health programs.

5.3.1 Allowed Interventions – N/A

5.3.2 Prohibited Interventions – N/A

5.3 Lifestyle Considerations

None.

5.4 Intervention Discontinuation

Withdrawal of consent will result in true study discontinuation with no interview or assessment performed. Any information collected before withdrawal will be kept as part of the subject's record. The study will document the patient's reason for withdrawal, if available, to track for study purposes.

Patients can also be withdrawn by the study if they become ineligible after consent. These reasons include (1) surgery cancelation or rescheduling with a greater than 6-month delay, (2) demonstrating substantial cognitive impairment at two time points as evidenced by lack of orientation to person, place, or time or lack of ability to repeat back and answer questions; or (3) displays or shows evidence of psychotic symptoms, (4) fails to follow instructions of the researchers.

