2 OUTCOMES^{CT.GOV;ERSCH}

2.1 Primary Outcome

The primary goal of this trial is to test initial efficacy of health coaching relative to brief advice. The primary outcome that this trial is powered to detect is change in alcohol use (defined as average weekly drinking) from baseline to one month follow-up (pre-operative outcome) and from baseline to the four month follow-up (post-operative outcome) in the Health Coaching condition relative to the brief advice condition.

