6 STUDY PROCEDURES^{ERSCH}

For Phase 3 we will conduct a randomized pilot trial test of Health Coaching and Brief Advice interventions to reduce alcohol use prior to elective surgery. The goal of the pilot trial is to assess the initial efficacy of Health Coaching relative to the Brief Advice Intervention and determine initial acceptability, feasibility, and fidelity of both conditions. Participants have a choice of intervention modality and they will either take place in-person or as a virtual meeting using an encrypted, university-supported virtual meeting platform. The in-person meetings will take place at either the Rachel Upjohn Building, in MCRU research space, or at a building within UM or UMHS, or a mutually agreed upon location within the community. If a participant cannot complete all study activities during one visit or virtual visit, we will allow participants to set an appointment to complete these activities within three days. This study has one baseline assessment. Follow-up surveys will take place at one-month post-baseline (Follow up 1; one week pre-surgery) and at four-months post-baseline (Follow-up 2; 3-months post-surgery).

Randomization

Participants will be urn randomized to study condition using computerized random number generator. Groups will be balanced based on gender.

Assessment and Measures

Baseline assessment will take place at least four weeks prior to surgery. The baseline assessment will take approximately 40 minutes to complete. Thus, the first appointment will take up to 120 minutes for those randomized to health coaching (15 minutes to

review the consent form; 40 minutes for baseline assessment; 50 minutes for the intervention; 10 minutes for the post-intervention feedback; and 5 minutes to provide the incentive) or 75 minutes for those assigned to receive brief advice (15 minutes to review the consent form; 40 minutes for baseline assessment; and 10 minutes for the brief advice intervention and 10 minutes for intervention feedback evaluation).

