6.1 Schedule of Activities

Table 1. Example of a Schedule of Activities (template)

	Pre-screening (Pre-consent)		Baseline Week 1, Day 1	Intervention ¹ Week 3	Intervention Week 5	Intervention Week 6 (day or surgery)	Intervention Week 18	Intervention Week 19	Withdrawal ⁸
EMR Review eligibility	X								
Eligibility confirmation	X								
Informed consent			X						
Demographics			X						
Outcome Evaluation									
Self-report Alcohol Use			X		X		X		
Alcohol and drug use biomarkers (Urine drug screen and blood draw)						X			
Self-report Drug use			X		X		X		
Mediators and moderators			X		X		X		
Self-report Health and functioning assessment			X		X		X		
Randomization			X						
Experimental Interventions and intervention evaluations			X	X					
EMR review							X		
Qualitative Exit Interview								X	
Event reporting		X	X	X	X	X	X	X	X

Note. All self-report measures are listed in the assessment section

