6.2.5 Outcome Assessments

The change alcohol use and acceptability assessments will occur at three times throughout the study: baseline, one-month post-baseline, and four-months post-baseline. See List of Study Activities Table. We will verify alcohol and drug use reports through a blood draw and urine drug screen conducted on the day of surgery that will undergo lab testing for drug/alcohol biomarkers.

Qualitative Interviews

A total of 20 patients, 10 from each intervention condition, will be selected (based on response vs. non-response to intervention. Response is defined as an alcohol use reduction of greater than one standard deviation from the mean between baseline and final follow-up. Non-response is defined as any increase in alcohol use between baseline and final follow-up or no change in alcohol use. These participants will be asked to complete exit interviews regarding their experience. Qualitative interviews with patients occur during a single interaction with research staff. Qualitative interviews will be audio recorded. We will initially focus our patient interviews on what factors led to change or lack of change in alcohol use, and how the intervention played a role in these changes, and how the intervention could be improved.

6.2.6 *Withdrawal*

If subjects withdraw or decline to finish treatment, we will make every effort to gather primary outcome data at regularly scheduled follow-ups. We will also query for an adverse event over the phone or in person. For subjects who wish to withdraw completely from the study, we will make every effort to collect the data as soon as possible – i.e. when the individual lets you know of their decision to withdraw. We will continue to use data that was obtained prior to withdrawal date unless the participant asks for it to be destroyed. The data will be kept secure until it is destroyed.

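### A tolerated surgery delay of up to 6 months lets the four-month survey, labelled post-operative, fall before the operation, and the plan does not say which survey clock governs

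*Combined protocol and SAP*

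**What the plan says.** - **Withdrawal (Section 5.4).** "Patients can also be withdrawn by the study if they become ineligible after consent", and the reasons given include "surgery cancelation or rescheduling with a greater than 6-month delay". No other reason listed there concerns the surgery date.
- **Primary outcome (Section 2.1).** One of the two primary contrasts is the change "from baseline to the four month follow-up (post-operative outcome".
- **Survey timing from baseline (Section 6.2.5).** Outcome assessments are at "baseline, one-month post-baseline, and four-months post-baseline", with no reference to surgery.
- **Survey timing from both anchors (Section 6).** The first follow-up is "at one-month post-baseline (Follow up 1; one week pre-surgery" and the second is "at four-months post-baseline (Follow-up 2; 3-months post-surgery". Section 6.2.2 repeats this pairing.
- **Survey timing from surgery (Section 5, Health Coaching).** The follow-ups are one week before and one month after surgery.
- **Table 1 (Section 6.1).** The surgery column reads "Intervention Week 6 (day or surgery". Self-reported alcohol use is collected at baseline, Week 5 and Week 18.
- **Analysis (Sections 8.2.1 and 8.2.2).** The GEE model uses all available data. Surgery type is a covariate; whether surgery has taken place is not mentioned.

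**The concern.** The tolerated delay is longer than the whole four-month follow-up. A patient can be postponed well past the last survey, remain in the study, and contribute a value that Section 2.1 calls post-operative. Nothing says that the survey moves with the operation, or how a survey completed before surgery is to be classified.

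This affects what the result means. The interventions aim at abstinence for 4 weeks before and 6 weeks after surgery (Protocol Summary). In Week 18 a patient operated on in Week 6 is past that period, while a patient whose surgery has moved to Week 20 is inside the pre-operative part of it. The four-month contrast would pool the two under one label.

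A second issue follows from the same clause. Patients whose surgery is cancelled or delayed by more than 6 months can be withdrawn after randomisation, although both surveys dated from baseline could still be obtained from them.

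**Working it through.** **Inputs.** Surgery in Week 6, surveys in Weeks 5 and 18 (Table 1). Delay limit of 6 months (Section 5.4). Final survey four months after baseline, equated with three months after surgery (Sections 6 and 6.2.2). Conversion: 1 month = 30.44 days.

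**1. The plan's own timing.** Week 18 − Week 6 = 12 weeks = 84 days, and 84 / 30.44 = 2.8 months after surgery. Week 1 to Week 18 is 17 × 7 = 119 days, and 119 / 30.44 = 3.9 months after baseline. The two descriptions of the final survey agree, provided surgery takes place in about Week 6.

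**2. The delay limit in weeks.** 6 × 30.44 / 7 = 26.1 weeks.

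**3. Effect of a delay of d weeks.** Surgery moves to Week 6 + d. On the baseline clock the final survey precedes surgery when 6 + d > 18, that is, d > 12. On a surgery clock the final survey moves to Week 18 + d. Follow-up 1 in Week 5 falls 1 + d weeks before surgery.

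| Delay (weeks) | Surgery | Final survey, baseline clock | Final survey, surgery clock | Follow-up 1 |
|---|---|---|---|---|
| 0 | Week 6 | 12 weeks after surgery | Week 18 | 1 week before surgery |
| 12 | Week 18 | same week as surgery | Week 30 | 13 weeks before |
| 20 | Week 26 | 8 weeks before surgery | Week 38 | 21 weeks before |
| 26 | Week 32 | 14 weeks before surgery | Week 44 | 27 weeks before |

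The exposed range is a delay of more than 12 and up to 26 weeks. Table 1 is titled as an example, so the text can be used instead: three months is 3 × 30.44 / 7 = 13.0 weeks, and the range becomes about 13 to 26 weeks. The conclusion is the same.

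**4. The surgery clock at the limit.** Week 32 + 12 or 13 weeks = Week 44 or 45. That is 43 to 44 weeks after Week 1, or 301 to 308 days, and 301 / 30.44 = 9.9 to 308 / 30.44 = 10.1 months after baseline.

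**5. The third anchor.** One month after surgery, as in the Health Coaching text, is Week 6 + 30.44 / 7 = about Week 10. That is some 8 weeks before Week 18 even with no delay.

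**6. Beyond the limit.** With a delay over 26 weeks the new date is after Week 32. Both surveys, in Weeks 5 and 18, could be completed before it.

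**The case against.** The strongest reply is that the real fault is the conflicting survey anchor, and that on a surgery clock the final survey is post-operative by construction. That is right about the root cause, and the fix starts there. It does not rescue the plan as written: Sections 2.1 and 6.2.5 date the outcome from baseline, and a survey that follows the operation can be about 10 months out.

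It can also be said that Section 5.4 is permissive, that its list may not be exhaustive, that this is a pilot with hypothesis testing called exploratory, and that Section 8.2.2 defines the outcome without the post-operative label. All of this stands. Retention below 6 months is an inference, though the natural one. The randomised comparison at a common time from baseline remains valid; what fails is its description.

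A reader might infer more than the documents support:

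- **That the 6-month limit serves no purpose.** Day-of-surgery biomarkers and the perioperative chart review depend on an operation taking place, so some limit on delay has an evident reason. It is not a reason to stop the drinking surveys.
- **That a patient enrolled near the 120-day limit is mislabelled after a delay of about two days.** Four months is 122 days, so the subtraction is right. But 120 days is an eligibility window for surgery or pre-operative assessment, and Health Coaching is to start about four weeks before surgery. Only the wording that baseline is at least four weeks ahead permits this case, so it is an extreme.
- **That a particular number of patients is affected.** Assuming that 5% to 10% are delayed beyond 12 weeks would give 4.5 to 9 of 90, but nothing in the documents supports that rate.

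**Conclusion.** The point holds in this form: following the stated rules, a retained patient delayed by more than about 12 and up to 26 weeks supplies a value labelled post-operative before any operation, by as much as about 14 weeks. The one-week pre-surgery label of Follow-up 1 also fails for delayed patients. Neither clock makes the final survey both a four-month and a post-operative outcome for everyone.

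This rests on the baseline dating in Sections 2.1 and 6.2.5, on surgery planned for about Week 6, and on reading Section 5.4 as keeping patients with shorter delays. How often it would happen cannot be calculated. It should be corrected because it concerns a primary time point and the avoidable loss of randomised patients, and because correction is cheap. It does not show that the randomised comparison is invalid.

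**What to change.** 1. Reconcile the survey anchor across Sections 2.1, 5, 5.4, 6, 6.1, 6.2.2 and 6.2.5.
2. For the primary drinking outcome, use the baseline clock, and call the time points the one-month and four-month outcomes in all randomised patients.
3. State in Section 5.4 that cancellation or rescheduling of surgery does not end survey follow-up. These patients complete both surveys and stay in the primary analysis; they may lack biomarkers and perioperative chart data. This concerns data collection only and fits the effort to obtain primary outcome data described in Section 6.2.6.
4. From the surgery details tracked in REDCap (Section 4.4), derive whether surgery took place before each survey, and report this by arm. Section 4.4 has the date confirmed at the time of the intervention, so the record must be updated to the actual date.
5. Treat any analysis limited to operated patients as exploratory. Being operated on is a post-randomisation event and drinking could influence it, so the arms may no longer be comparable.

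The cost is protocol and analysis wording, one yes/no variable per survey, and keeping the surgery date current. The downside is that the four-month result can no longer be called post-operative for everyone.
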